7.5 Analysis Plan

Aim 1: To determine whether telehealth PC is equivalent to in-person PC for improving patients' QOL

We will begin with descriptive and graphical summaries of the endpoints to evaluate whether normality assumption is reasonable or if transformation is necessary. As the goal of the proposed study is to establish that patient-reported QOL with telehealth PC is equivalent to in-person PC, statistical testing for equivalence of the primary outcome will be two-sided with an alpha level of 0.05. We will use analysis of covariance (ANCOVA) models controlling for baseline values, and demographic and clinical factors (as necessary for any imbalances in baseline variables) to assess the effect of telehealth PC compared to in- person PC on QOL at 24 weeks. We will also use linear mixed models of the longitudinal data, allowing us to account for dependency among means over time and to control for demographic and clinical factors (as necessary for any imbalances in baseline variables) when examining change between groups in QOL across multiple time points (i.e., baseline, week-12, week-24, week-36, and week-48). Lastly, we will test Heterogeneity of Treatment Effect (HTE) based on age, gender, race, computer experience, and enrollment of caregivers using interaction terms in the linear mixed models (see HTE analysis plan).

We will use ANCOVA models controlling for baseline values, and demographic and clinical factors as necessary to assess the effect of telehealth PC compared to in-person PC on patient mood (HADS, PHQ-9), and coping strategies (Brief Cope subscales) at 24 weeks. We will then utilize linear mixed models of the longitudinal data as described above to examine change in depression and coping between groups across multiple time points. Lastly, we will also compare illness understanding as measured by the PTPQ between the two groups through week-24, analyzing items using linear or logistic regression as appropriate and adjusting for demographic and clinical factors as necessary. The patient's final post-baseline PTPQ assessment within 24 weeks will be used.

Aim 2: To determine whether telehealth PC is equivalent to in-person PC with respect to patient-clinician communication about EOL care preferences and length of stay in hospice

We will examine patient-report of discussing EOL care preference with their clinicians using the following item: "Have you and your doctors discussed any particular wishes you have about the care you would want to receive if you were dying?" (Yes/No). Although patients will complete this measure repeatedly during the study, we will use the final assessment for this analysis. We will assess differences between study groups in the rate of patients reporting "Yes" to this item using a Fisher's exact test with a two-sided alpha of 0.05 (equivalence margin=8%). We will then use a logistic regression model adjusting for any demographic and clinical factors that are imbalanced to assess differences in this dichotomous outcome between the two groups.

Additionally, we will assess the equivalence of hospice length-of-stay between telehealth PC and in-person PC with an equivalence margin of 6 days. We will use linear regression models adjusting for demographic and clinical factors as necessary to compare hospice length-of-stay between telehealth PC and in-person PC. Although hospice length-of-stay is not normally distributed, based on a sample size of 1250, the means would have a normal distribution (central limit theorem). Nonetheless, we will also perform poisson regression or Wilcoxon rank sum test to compare our results to those obtained with linear regression.

Aim 3: To compare the effect of telehealth versus in-person PC on caregiver participation in PC visits and outcomes

We hypothesize that caregivers receiving telehealth PC will participate in a higher proportion of their loved ones' PC visits during the study and that the participating caregiver will report better QOL at 24 weeks compared to those randomized to in-person PC (superiority aim). We will compare rates of caregivers' participation in PC visits between the two groups using mixed logistic models in to account for correlation between multiple PC visits for each caregiver (controlling for any imbalances in demographic and clinical factors). In addition, we will compare caregiver QOL (CARGOQOL) at week-24 between the study groups using ANCOVA adjusting for baseline values and any imbalances in clinical and demographic factors. We will also use linear mixed models of the longitudinal data to account for dependency among means over time and to control for demographic and clinical factors (as necessary for any baseline imbalances) when examining change between groups in QOL across multiple time points (i.e., baseline, week-12, week-24, week-36, and week-48).

We will compare caregiver mood on the HADS at week-24 between groups using ANCOVA models as described previously. We will then evaluate linear mixed models of the longitudinal data as described above to examine change in caregiver depression and anxiety symptoms between groups across multiple time points. To compare caregiver illness understanding (as measured by the PTPQ) within 24 weeks between groups, we will analyze items using linear or logistic regression analyses as appropriate to adjust for clinical and demographic variables. The caregiver's final post-baseline PTPQ assessment within 24 weeks will be used. Lastly, we will compare caregivers' perception of quality of care at the EOL (per the After Death Assessment) between the two groups using ANCOVA as described previously.

Specific Aim 4: To compare patient and caregiver satisfaction with telehealth PC versus in-person PC

We will measure patient and caregiver satisfaction with the intervention using The Satisfaction and Care Delivery Questionnaire. Although patients and caregivers will complete this measure repeatedly during the study, we will use the final assessment for this analysis. We will compare scores between the telehealth PC and the in-person PC using ANCOVA adjusting for study site and any imbalances between the two groups.

Tests for Heterogeneity. We will analyze Heterogeneity of Treatment Effect (HTE) by testing for interaction effects between the intervention group and the following variables: patient age ($>65, \le65$), gender (male vs. female), race/ethnicity (White vs. Black; White

vs. Asian; Non-Hispanic White vs. Hispanic/Latino), computer experience (yes vs. no), and enrollment of caregiver (yes vs. no). The interaction terms will be tested in the linear mixed effects models examining patient QOL, depression, hospice length-of-stay as well as in a logistic regression model examining EOL communication. Observing an interaction effect (P < 0.15), ⁵⁴ we will conduct separate subgroup analyses to assess for HTE of the telehealth intervention compared to in-person PC. Since this trial is testing the modality of delivery of PC (telehealth vs. in-person), all HTE analyses are considered exploratory and hypothesis-generating.

Prior studies have found that age, gender, and race can moderate the impact of PC in patients with cancer. 55,56 However, it remains unclear whether these factors would contribute to HTE of the telehealth intervention versus in-person PC. While studies utilizing mobile and computer technology have not shown that computer experience moderates the effect of interventions with adequate training, 57,58 we will specifically assess HTE based on computer experience to ensure generalizability of our findings. Lastly, since the use of telehealth may facilitate the presence of a caregiver during the appointments, we will also examine whether the enrollment of a caregiver contributes to the HTE of the telehealth PC compared to in-person PC.

Multiple testing: For all significance tests of secondary outcomes, we will use the false discovery rate (FDR) control method to address the issue of multiple tests. We selected an FDR of 0.15, which denotes the acceptable percentage of results that potentially represent false positives. Analyses of exploratory outcomes will not be adjusted for multiple comparisons, and presented results will emphasize estimates and confidence intervals.

7.3.1 Stratification Factors and Intervention Allocation Plan for Randomized Studies. Patients will be randomized between study groups using block randomization with stratification by study site.

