7.4 Sample Size and Power Calculation

The primary endpoint of the study is to establish that telehealth PC is equivalent to inperson PC in patient-reported QOL at week-24, as measured by the FACT-L. Although the primary endpoints in our previous studies assessed the change in FACT-L from baseline to week-12, we chose to focus on QOL at 24 weeks as the life-expectancy of patients with advanced lung cancer has increased over the last few years. In our most recent randomized trial of early integrated PC versus standard oncology care, we observed a 7.5 (SD = 17.0) point difference in the FACT-L at week-24 favoring the early integrated PC group. Thus, we chose a conservative equivalence margin of 4 points, which is slightly more than 50% of the previously observed advantage with early integrated PC compared to oncology care alone. As a 6-point difference in FACT-L score is considered the lowest range of a clinically meaningful difference, our equivalence margin would not reach the threshold of clinically meaningful difference in QOL between telehealth PC and in-person PC. 53 With 469 patients per group, we would have 95% power to establish the equivalence of telehealth PC compared to in-person PC on the FACT-L, with a two-sided alpha of 0.05, and an equivalence margin of 4 points. In our recent trial, we observed 25% missing data at 24 weeks. Therefore, we increased our sample size to 625 per group (total sample size = 1250 patients) to ensure we have adequate power to assess the equivalence of telehealth PC compared to in-person PC. Importantly, we chose to be conservative in estimating the sample size of this trial given the proposed testing of equivalence of telehealth PC to in-person PC on secondary outcomes as well as the planned subgroup analyses.

The proposed study will also have adequate power to assess for equivalence of telehealth PC compared to in-person PC in EOL communication and hospice length-of-stay. With a sample size of 1250, we will have 89% power, with a two-sided alpha of 0.05, to assess the equivalence of telehealth to in-person PC on patient-reported EOL communication with an equivalence margin of 8%, assuming the rate of EOL communication in the in-person PC group is 30% (based on our recent trial). With this sample size, we will also have 94% power to establish the equivalence of telehealth PC compared to in-person PC in hospice length-of-stay, with a two-sided alpha of 0.05, and an equivalence margin of 6

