Sample size calculations were performed to demonstrate equivalence with a margin of ±4 points on the FACT-L at week 24, assuming a standard deviation of 17.5 points and a between-group difference of 0 points. 469 patients per group would achieve 95% power at a 5% significance level using two one-sided, equal-variance t-tests. To account for an anticipated 33% missing data proportion at week 24 due to loss-to-follow-up, withdrawal, or death, enrollment of 625 per group (1250 total) was planned.

9. General Statistical Considerations

Statistical Software

All statistical analyses will be performed using SAS (SAS Institute Inc., NC, USA) and R (R Foundation for Statistical Computing, Vienna, Austria).

Analysis Population

The primary analyses will be conducted according to the intention-to-treat principle. All randomized patients will be included and analyzed in the group to which they were initially randomized, regardless of intervention adherence. To address intervention contamination introduced during the COVID-19 pandemic, sensitivity analyses will be conducted to ensure the validity of the study findings. These sensitivity analyses may include per-protocol analysis, contamination adjusted intention-to-treat analysis using instrumental variables, and inverse probability weighting analyses to provide robust statistical estimates for the primary and secondary outcomes in this trial.

Patient Disposition

The flow of patients through the study will be demonstrated using a flow diagram, consistent with the Consolidated Standards of Reporting Trials (CONSORT) statement. This diagram will display number of patients assessed for eligibility, the number of patients who enrolled and randomized in the study and the number of patients who were excluded or otherwise not enrolled. For enrolled patients, the study group allocation will be displayed, along with the number of patients who complete follow-up assessments at each time point. The number of patients in each group who were lost to follow-up or otherwise excluded from analysis will be displayed.

Baseline Characteristics

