Baseline characteristics including demographic information, smoking status, cancer type, comorbidities, and baseline PROs score will be summarized by intervention group using descriptive statistics and visual displays. Descriptive statistics for continuous variables will include the number of subjects, mean, standard deviation, median, first and third quartiles, and minimum and maximum values for the observed value. Frequencies and percentages will be calculated for categorical variables.

Adjustment of the Intervention Effect

The primary analyses for all outcomes will be unadjusted except when adjustment for baseline outcome values is pre-specified. For the primary outcome, a sensitivity analysis will evaluate the impact of adjustment for study site, the randomization stratification variable (n=20 sites). Adjustment for study site via a main effect or random effect will be considered. Small strata will be combined as needed to ensure numeric stability of model estimates.

For all outcomes, sensitivity analyses will adjust for baseline characteristics that are imbalanced between treatment groups, if needed. Imbalanced characteristics will be identified *a priori* by examining the distributions of baseline characteristics known to be associated with the primary and secondary outcomes by intervention group. Characteristics that are imbalanced to an extent that is considered clinically meaningful will be included as main effects.

Significance Level and Multiplicity Adjustment

Statistical significance testing for equivalence of the primary outcome will use two one-sided tests, each with a type I error rate of 0.05. The Benjamini-Hochberg false discovery rate (FDR) control approach will be used to interpret results of significance tests of secondary outcomes with an FDR of 0.15. Analyses of exploratory outcomes will not be adjusted for multiple comparisons, and presented results will emphasize estimates and confidence intervals.

Scoring of Patient-Reported Outcomes

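### The protocol's two-sided 0.05 for the primary equivalence test is never reconciled with the SAP's 90% CI rule, and Fisher's exact test cannot establish the secondary equivalence claim

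*Protocol*

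**What the plan says.** **Primary outcome, protocol.** Section 7.5, Aim 1, states that "statistical testing for equivalence of the primary outcome will be two-sided with an alpha level of 0.05". Section 7.4 claims 95% power for 469 per group and ties that claim to the same alpha: "with a two-sided alpha of 0.05, and an equivalence margin of 4 points". Neither section names a confidence level or the two one-sided tests procedure (TOST).

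**Primary outcome, SAP.** Section 9 specifies "two one-sided tests, each with a type I error rate of 0.05". Section 10 turns this into a rule: equivalence holds if the 90% CI for the difference in means lies inside (-4, 4), and the p-value is the larger of the two one-sided p-values. Section 8 gives the same 469 per group and 95% power for two one-sided t-tests at 5%. The addendum lists later changes to the analysis plan; none concerns the primary alpha.

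**Standard deviation.** Protocol 7.4 cites an earlier trial: "we observed a 7.5 (SD = 17.0) point difference in the FACT-L at week-24 favoring the early integrated PC group". SAP section 8 sizes the trial "assuming a standard deviation of 17.5 points and a between-group difference of 0 points".

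**End-of-life communication.** Protocol 2.2.1 states an equivalence hypothesis with an 8% margin. Protocol 7.5, Aim 2, tests it "using a Fisher's exact test with a two-sided alpha of 0.05 (equivalence margin=8" percent). SAP section 10 instead uses two one-sided tests of the difference in proportions against -8% and +8%.

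**The concern.** A two-sided 0.05 is ordinarily reported as a 95% CI. Applied to an equivalence margin, that would require the 95% CI to lie inside ±4, which is stricter than the SAP's 90% CI. A reader who holds the trial to its protocol could then reject a claim of equivalence that the SAP accepts, on the primary outcome. The stated power would also belong to one rule and not the other.

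Fisher's exact test raises a different problem. Its null hypothesis is no difference, and the margin does not enter it. A non-significant result does not show that the rates are within 8 percentage points, and a significant one does not show that they are further apart than that.

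**Working it through.** **Inputs.** Margin 4 points, 469 per group and stated power 95% (protocol 7.4; SAP section 8). SD 17.0 (protocol 7.4) or 17.5 (SAP section 8). True difference 0 (SAP section 8; the protocol gives none, so 0 is assumed there too). The calculations ignore the precision gained from baseline adjustment.

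**Step 1: reproduce the stated power.** SE = SD × √(2/469). Equivalence power at a true difference of 0 is 2Φ(4/SE − z) − 1, with z = 1.645 for the 90% CI rule and 1.960 for a 95% CI rule.

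- SD 17.0: SE = 1.110 and 4/SE = 3.603. The 90% CI rule gives 2Φ(1.958) − 1 = 95.0%. The 95% CI rule gives 2Φ(1.643) − 1 = 90.0%.
- SD 17.5: SE = 1.143 and 4/SE = 3.500. The 90% CI rule gives 2Φ(1.855) − 1 = 93.6%. The 95% CI rule gives 2Φ(1.540) − 1 = 87.6%.

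Exact t-based calculations differ from these by at most 0.1 percentage point. The stated 95% is reproduced by the SAP's rule with the protocol's SD.

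**Step 2: where the two rules part.** The largest observed difference that passes is 4 − z × SE.

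| SD | 90% CI rule | 95% CI rule |
|---|---|---|
| 17.0 | 2.17 points | 1.82 points |
| 17.5 | 2.12 points | 1.76 points |

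An observed difference between the two limits in a row is equivalent under one rule and not under the other. To reach 95% power, a 95% CI rule would need 556 per group (SD 17.0) or 589 (SD 17.5). The SAP's rule at SD 17.5 would need 498.

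**Step 3: does 469 with 95% power reveal the intended rule?** It does not. The common formula for a two-sided 0.05 that counts only one margin gives n = 2 × 17.0² × (1.960 + 1.645)² / 4² = 469.4. TOST at 0.05 each with 95% power, splitting the 5% type II error over two margins, needs z values of 1.645 and 1.960. The one-margin formula needs 1.960 and 1.645. The sum is the same, so both lead to the same n.

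**Step 4: do the secondary power figures settle it?** Protocol 7.4 uses 1250 patients, so 625 per group.

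- Hospice stay (SD 30.0, margin 6 days, stated 94%): SE = 30 × √(2/625) = 1.697 and 6/SE = 3.536. TOST at 0.05 gives 2Φ(1.891) − 1 = 94.1%. The one-margin formula gives Φ(1.576) = 94.2%. Both fit.
- End-of-life communication (30%, margin 8%, stated 89%): SE = √(2 × 0.30 × 0.70/625) = 0.0259 and 0.08/SE = 3.086. TOST gives 2Φ(1.441) − 1 = 85.0% at 0.05, and 74.0% at 0.025. An ordinary two-sided 0.05 test of 30% against 22% gives 89.8%, which is the closest.

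So a two-sided alpha in this protocol cannot be assumed to be shorthand for TOST, nor can it be shown to mean a 95% CI.

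**Step 5: Fisher's exact test.** Suppose non-significance were read as equivalence. With true rates exactly at the margin, exact enumeration of the two binomial samples gives this probability of p > 0.05:

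| Per arm | 30% v 22% | 30% v 38% |
|---|---|---|
| 625 | 11.3% | 16.5% |
| 469 | 22.1% | 28.7% |

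TOST aims at a nominal 5%. By the normal approximation at 625 per arm, non-significance tolerates observed gaps up to 1.960 × 2.59 = 5.1 percentage points; TOST accepts only up to 8 − 1.645 × 2.59 = 3.7.

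**The case against.** The best defence is that the protocol never mentions a 95% CI. An equivalence test has two margins, and two-sided may simply distinguish it from non-inferiority. An equivalence test of overall size 0.05 against both margins is TOST, that is, the 90% CI rule. On that reading the SAP makes a loose sentence precise, and an analyst who follows the SAP has no choice of threshold left. This much stands: a reader might infer that the documents contradict each other, but they show only wording that can be read two ways and is nowhere reconciled.

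A reader might also infer that the 95% power fits only the SAP's rule. Step 3 shows that the 469 and 95% pair also comes from a one-margin formula at two-sided 0.05, and the SAP's rule falls to 93.6% at the SAP's own SD.

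The practical effect is limited. With a true difference of 0, SD 17.0 and 469 per group, an estimate falls in the disputed band in about 5% of trials. With all 625 per group observed, a 95% CI rule would still have about 97% power (SD 17.0) or 96% (SD 17.5). With 33% missing (625 × 0.67, about 419 per group), it would have about 85% or 82%.

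On Fisher's test, the SAP already has a sound replacement, and the protocol does not say that non-significance would be declared equivalence. The error rates in Step 5 are therefore conditional. The objection does not rescue the test itself, which has no way of using the margin quoted beside it.

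Protocol 7.5 also proposes to "evaluate whether normality assumption is reasonable or if transformation is necessary", which might suggest that the 4-point margin could lose its scale. That clause is a conditional check on the endpoints generally, and the SAP's primary model applies no transformation, so naming the scale is enough.

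**Conclusion.** The concern holds as two points about wording.

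1. The primary decision threshold is ambiguous between the documents. If the protocol's two-sided 0.05 means a 95% CI, conclusions differ for observed differences of about 1.82 to 2.17 points, and power is 90.0% at SD 17.0 or 87.6% at SD 17.5. If it means TOST of size 0.05, the rules agree, and only the SD separates 95.0% from 93.6%. These figures assume 469 per group, a true difference of 0 and no gain from baseline adjustment.
2. Fisher's exact test is the wrong tool for the equivalence hypothesis on end-of-life communication, and it conflicts with the SAP. This does not depend on how the alpha is read.

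The SAP's rules are sound on both points, so the documents should be aligned to them. Nothing here shows that the planned SAP analysis is invalid.

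**What to change.** Issue a dated clarification, as a protocol amendment or an SAP addendum entry, that does the following:

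- States that primary equivalence is judged by two one-sided tests at 0.05 each, that is, by the 90% CI for the difference on the untransformed FACT-L scale lying within -4 to 4.
- Commits to reporting the 95% CI alongside. The SAP describes enrolment in the past tense and its last addendum entry responds to peer review, so the clarification is retrospective and adopts the more lenient of two readings. Showing both intervals lets the reader see whether the choice mattered.
- Replaces Fisher's exact test in protocol 7.5, Aim 2, with the SAP's two one-sided tests against ±8 percentage points, subject to the SAP's multiplicity rule for secondary outcomes.
- Gives the power with its rule and SD: under two one-sided tests at 0.05 with 469 per group, 95.0% at SD 17.0 and 93.6% at SD 17.5.

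The cost is wording and one extra interval in the report. No new data are needed, and the SAP's primary analysis does not change.

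### The exploratory arm-by-age interaction is tested only with age cut at 65; if effect modification is roughly linear in age, that costs about 15 points of power for a 4-point FACT-L difference (about 10 to 18.5 under other assumptions)

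*Protocol*

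**What the plan says.** Under Tests for Heterogeneity, Protocol 7.5 plans interactions between arm and five patient variables. Age appears as "patient age ($>65, \le65$), gender (male vs. female", that is, as two groups split at 65. On the models it says: "The interaction terms will be tested in the linear mixed effects models examining patient QOL", followed by depression and hospice stay, with a logistic model for EOL communication. The follow-on step is conditional: "Observing an interaction effect (P < 0.15") leads to separate subgroup analyses.

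The reason for including age is this: "Prior studies have found that age, gender, and race can moderate the impact of PC in patients with cancer". The section also fixes the status of the work: "all HTE analyses are considered exploratory and hypothesis-generating".

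Neither document plans an interaction with age in years, explains the choice of 65, or states power for any interaction. The SAP text has no section on heterogeneity of effect, so Protocol 7.5 is the only specification.

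**The concern.** Of the five listed modifiers, age is the one that is plainly a measured quantity. Splitting it at 65 treats patients of 66 and 85 as alike and patients of 65 and 66 as different. If the arm difference drifts steadily with age, the split discards part of the information on that drift. With normal age and a median split it keeps about 64%.

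The interaction test also decides whether age is examined further, because subgroup analyses follow only when P is below 0.15. A missed interaction therefore closes the question of age for that outcome. Protocol 7.4 says the sample size was set conservatively partly with the planned subgroup analyses in mind, so it is reasonable to ask that the age test use the data efficiently.

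**Working it through.** **Inputs from the documents**
- Margin, used here as the size of interaction to detect: "Thus, we chose a conservative equivalence margin of 4 points" (Protocol 7.4).
- SD: "we observed a 7.5 (SD = 17.0) point difference in the FACT-L at week-24" (Protocol 7.4). SAP section 8 differs: "assuming a standard deviation of 17.5 points".
- Evaluable patients: 469 per group, N = 938 (Protocol 7.4).
- Interaction threshold: two-sided P < 0.15, so z = 1.440 (Protocol 7.5).

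**Assumptions the documents do not supply**
- Age is roughly normal and about half the patients are over 65. The documents give only the eligibility limit of 18 years.
- Effect modification is linear in age.
- The planned mixed model is approximated by a week-24 comparison.
- The 4 points are a difference in treatment effect between the two age groups. The protocol's margin concerns the overall arm difference, so this borrows its size only.

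**Step 1: reproduce the plan's own figure.** For the primary equivalence test, SE = 17 × √(2/469) = 1.110. With two one-sided tests at 0.05 and a true difference of 0, power = 2Φ(4/1.110 − 1.645) − 1 = 2Φ(1.958) − 1 = 95.0%. This matches the stated 95%. The SAP's SD of 17.5 gives 93.6%.

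**Step 2: interaction with age cut at the median.** SE of the difference between the two subgroup effects = 4 × 17/√938 = 2.22. Noncentrality = 4/2.22 = 1.80. Power = Φ(1.80 − 1.44) + Φ(−1.80 − 1.44) = 64.2%.

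**Step 3: the same linear interaction with age in years.** The correlation between normal age and its median split is √(2/π) = 0.798, and 0.798² = 0.637 is the share of information kept. Noncentrality = 1.80/0.798 = 2.26. Power = Φ(2.26 − 1.44) + Φ(−2.26 − 1.44) = 79.4%. The loss is 15.2 points. A simulation of 10,000 trials gave 63.8% and 79.1%.

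**Step 4: vary one assumption at a time** (4 points, P < 0.15, SD 17 and N = 938 unless stated)

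| Case | Cut at 65 | Age in years | Loss (points) |
|---|---|---|---|
| Base case | 64.2% | 79.4% | 15.2 |
| SD 17.5 | 62.3% | 77.5% | 15.2 |
| 40% or 60% over 65 | 62.8% | 78.8% | 16.0 |
| 30% or 70% over 65 | 58.5% | 76.9% | 18.5 |
| All 1250 analysed | 73.9% | 87.8% | 13.9 |
| Baseline correlation 0.5 | 73.9% | 87.9% | 13.9 |
| Baseline correlation 0.6 | 79.2% | 91.7% | 12.5 |
| Baseline correlation 0.7 | 86.1% | 95.7% | 9.7 |
| Age uniform | 64.2% | 73.9% | 9.7 |
| True effect a step at 65 | 64.2% | 50.1% | −14.1 (cut better) |

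The baseline-correlation rows replace the SD by 17 × √(1 − r²). For other interaction sizes in the base case, 3 points gives 47% against 60%, and 5 points gives 79% against 92%.

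**The case against.** The strongest defence is that the cut may be right. If the effect really changes at 65, the two-group test has 64% power and a linear term only 50%, so a reader who infers that the cut brings no gain under any circumstances goes too far. The documents posit no such step, but they do not exclude one. The cut is also fixed in advance, and it defines the groups for the follow-on analyses. Protocol 7.5 cites earlier studies on moderation by age, gender and race. Whether they support 65 cannot be seen from the documents.

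Three other readings are tempting and are not supported:

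- **That the age test carries the trial's generalisability question.** Protocol 7.5 attaches generalisability to computer experience. For age, gender and race it says only that their role in telehealth versus in-person care is unclear.
- **That 15 points is a fixed property of the plan.** It depends on an age distribution and a linear form that the documents do not give. The planned QOL model is longitudinal and uses baseline information, which lowers the loss in the cases computed.
- **That the same loss is shown for all four models.** Power was worked out only for FACT-L. The loss of information applies in kind to depression, hospice stay and EOL communication, but no power was computed for them.

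The exploratory label and the liberal 0.15 threshold do limit the consequence. They do not make the less efficient test preferable, since an analysis meant to generate hypotheses depends on its sensitivity.

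**Conclusion.** The point holds as a minor, conditional improvement. The only planned age interaction uses a cut at 65 that neither document justifies. If effect modification is roughly linear, the cut lowers power in the base case from about 79% to 64% for a 4-point difference in treatment effect, and the loss runs from about 10 to 18.5 points across the other linear cases tried. The direction reverses if the true effect is a step at 65. A reader might infer that this weakens the trial's main findings. It does not, because the interaction tests play no part in the primary equivalence test or the secondary comparisons.

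**What to change.** In Protocol 7.5, test the arm-by-age interaction with age in years. Prespecify one quadratic or spline term to check linearity, so that the check does not become a search. Report the telehealth minus in-person difference with its CI at several ages, for example 55, 65 and 75. Keep the >65 versus ≤65 result beside it, because that is the better test if the effect is a step.

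The cost is one extra form of a variable in models already planned, and no new patients or assessments. The downside is reliance on a near-linear form, with the loss shown above if that form is badly wrong. Timing also matters: the SAP addendum entries run from January to April 2024 and one responds to peer review. A change made after SAP finalisation should therefore be entered as a dated addition and labelled as such, not presented as the original specification.
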